12.3 Lenalidomide administration

Lenalidomide will be given on days 1-21 in 28-day-cycles. The dose will be 25mg unless reduced renal function (see 10.3.1). If the dose is missed, it should be taken as soon as possible within 12 hours. If over 12 hours have passed, the dose must be skipped. The subject should never take 2 doses at the same time.

12.3.1 Starting lenalidomide in renal failure

| Category | Renal Function (Cockcroft-Gault) | Dose in MM |
|---------------------------|---|---|
| Moderate Renal Impairment | CLcr 30-50 mL/min | 10 mg Every 24 hours |
| Severe Renal Impairment | CLcr < 30 mL/min (not requiring dialysis) | 15 mg Every 48 hours |
| End Stage Renal Disease | CLcr < 30 mL/min (requiring dialysis) | 5 mg Once daily. On dialysis days, administer the dose following dialysis. |

If the dose is tolerated, it can be escalated according to local procedures.

12.3.2 Dose modification guidelines for lenalidomide

The dose modification guidelines as summarized below are recommended to manage both hematological and non-hematological toxicity. Local investigators can decide to not follow this dose modifications if they feel it is not in the best medical interest of the patient.

Hematological toxicity present at start of study should not lead to dose reduction.

| Platelet counts | |
|---|--|
| Thrombocytopenia | |
| When Platelets | Recommended Course |
| Fall to <30,000/mcL | Interrupt lenalidomide treatment, follow CBC weekly |
| Return to \geq 30,000/mcL | Resume lenalidomide at next lower dose. Do not dose below 2.5 mg daily |
| For each subsequent drop <30,000/mcL | Interrupt lenalidomide treatment |
| Return to \geq 30,000/mcL | Resume lenalidomide at next lower dose. Do not dose below 2.5 mg daily |
| Absolute Neutrophil counts (ANC) | |
| Neutropenia | |
| When Neutrophils | Recommended Course |
| Fall to <1000/mcL | Interrupt lenalidomide treatment, follow CBC weekly |
| Return to \geq 1,000/mcL and neutropenia is the only toxicity | Resume lenalidomide at 25 mg daily or initial starting dose |
| Return to \geq 1,000/mcL and if other toxicity | Resume lenalidomide at next lower dose. Do not dose below 2.5 mg daily |
| For each subsequent drop <1,000/mcL | Interrupt lenalidomide treatment |
| Return to \geq 1,000/mcL | Resume lenalidomide at next lower dose. Do not dose below 2.5 mg daily |

12.4 Lenalidomide treatment after the four KRd cycles

Lenalidomide will be given according to the approved maintenance label for post-transplant patients, i.e. 10-15 mg daily continuously.

12.5 Dexamethasone administration

Dexamethasone will be given on days 1, 8, 15 and 22 in cycles of 28 days, and a dose of 40 mg PO. For subjects aged > 75 years, a daily low-dose dexamethasone dose of 20 mg is recommended.

For adverse events considered to be possibly due to dexamethasone treatment, the following dose reduction levels should be used:

| Dose Level | Dexamethasone dose (PO) |
|-------------------|--------------------------------|
| 0 | 40 mg |
| -1 | 20 mg |
| -2 | 12 mg |
| -3 | 0 mg |

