| 
Study Endpoints
 
Primary:
 
 - Proportion of PET-CT positivity after standard first line therapy - Change from PET-CT positivity to PET-CT negativity after 4 cycles of KRd consolidation. 
Secondary:
 
 - MRD negativity by 8-colour EuroFlow after 4 cycles of KRD consolidation. - Safety - Overall response rate - Progression-free survival (PFS) - Time to next treatment (TTNT) - Overall survival (OS) - Quality of life during and after KRD consolidation |
| 
Treatment schedule
 
Four cycles of Carfilzomib-Lenalidomide-Dexamethason
 
The carfilzomib dose is 20-20-36-36-36-36 mg/m² on day 1, 2, 8, 9, 15 and 16 in the first cycle. It will be increased to 36 mg/m² on days 1, 2, 8, 9, 15 and 16 in cycles 2-4.
 
The oral dexamethasone dose is 40 mg weekly throughout the study for patients under 75 years of age. 20 mg for patients over 75 years of age.
 
The Revlimid dose is 25 mg on days 1-21 in every cycle.
 |

Inclusion criteria (selected)

1. Prior confirmed diagnosis of multiple myeloma (2014).
2. Received standard first line treatment with at least partial response. Standard first line treatment is defined as VRD, VTD or VCD followed by ASCT, with or without lenalidomide maintenance
3. Carfilzomib naïve
4. Eastern Cooperative Oncology Group (ECOG) performance status 0-2.
5. Absolute neutrophil count (ANC) $\geq 0,5 \times 10^9/L$ and platelet count $>35 \times 10^9/L$.
6. At least very good partial remission (VGPR) from first line treatment

Exclusion criteria (selected)

1. Change of first line treatment because of stable or progressive disease.
2. Major surgery within 28 days before enrollment.
3. Radiotherapy within 14 days before enrollment.
4. Glucocorticoid therapy within the 14 days prior to inclusion that exceeds a cumulative dose of 160 mg dexamethasone or 1000 mg prednisone.
5. Patients who started treatment more than 12 month before screening
6. Central nervous system involvement.
7. Uncontrolled heart disease, including congestive heart failure (NYHA III-IV), uncontrolled angina pectoris, uncontrolled conduction abnormalities, acute diffuse infiltrative pulmonary disease, pericardial disease or myocardial infarction within 6 months prior to enrollment
8. Uncontrolled hypertension or uncontrolled diabetes despite medication
9. Active hepatitis B or C infection or known human immunodeficiency virus (HIV) positivity.

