2.1.1 Carfilzomib dosing in this study

There are four phase 3 studies in multiple myeloma, three for relapsed/refractory patients: ASPIRE (NCT01080391, PX-171-009)(5), FOCUS (NCT01302392, PX-171-011)(4), ENDEAVOR (NCT01568866, 2011-003)(8) and one for newly diagnosed patients; CLARION (NCT01818752, 2012-005), all of these with twice weekly dosing. Phase 1b/2 study CHAMPION-1 is for relapsed or refractory patients to investigate higher doses of carfilzomib given once weekly (10).

The PX-171-007 phase 1b/2 study was the first to evaluate the maximum tolerated dose of twice-weekly single carfilzomib dosing for RRMM patients (11). Carfilzomib was given as monotherapy on days 1, 2, 8, 9, 15 and 16 in a 28-day cycle. Cycle 1 day 1-2 doses were 20 mg/m² followed by dose escalation to 36, 45, 56 and 70 mg/m². Carfilzomib was administered with low-dose dexamethasone 40 mg weekly at the 45 and 56 mg/m² dose levels. Dose limiting toxicities (DLT) were found in 2/33 subjects at dose 70 mg/m², grade 3 renal tubular necrosis and proteinuria. The MTD was therefore determined to be 56 mg/m². The most common AEs in this dose cohort were nausea, dyspnea, fatigue, pyrexia, thrombocytopenia and chills with a majority of grade 1-2. Overall response rate (ORR) with carfilzomib monotherapy 20/27 mg/m² in earlier phase 2 PX-171-003 study, where the majority of patients were IMiD and bortezomib refractory, was 23.7% (7). With 56 mg/m², ORR was 50% in a similar population. Based on this PX-171-007 study higher doses of carfilzomib on a twice-weekly schedule given over 30 minutes were well tolerated and effective with an acceptable safety profile and this led to the study CHAMPION-1 where higher once weekly dosing of carfilzomib was investigated.

In CHAMPION-1, a phase 1b/2 study for relapsed MM patients with 1-3 prior therapies, the dose-escalation part included the dose of 20 mg/m² on day 1 cycle 1 followed by test doses on days 8 and 15 of cycle 1 in 28-day cycles (10). The dose escalation was from 45 mg/m² to 56, 70 and 88 mg/m² on days 1, 8, 15 combined with dexamethasone 40 mg on days 1, 8, 15, 22 in cycles 1-8 and 1, 8, 15 from cycle 9 onwards. No DLTs were noticed at the dose levels of 45-70 mg/m², but 88 mg/m² produced two DLTs; grade 3 dyspnea and vomiting. In the expansion cohort, one additional grade 3 dyspnea was noticed. The MTD of once-weekly carfilzomib combined with dexamethasone was determined to be 70 mg/m². The CHAMPION-1

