8. STUDY POPULATION

8.1 Inclusion criteria

Each patient must meet all the following inclusion criteria to be enrolled in the study:

1. At least 18 years of age, with at least 6 months expected survival.
2. Prior confirmed diagnosis of multiple myeloma (2014) (16).
3. Received standard first line treatment with at least a very good partial response (VGPR), according to IMWGs criteria . Standard first line treatment is defined as

VRD, VTD or VCD followed by ASCT with or without lenalidomide maintenance initiated (Patients where the monoclonal component or dFLC increases during the period from best response to screening can be included if there is no progressive disease.)

4. Patients must be carfilzomib naïve.
5. A positive PET-CT result from central reviewer in the screening period

6. Successful FISH evaluation performed with available results
7. Voluntary written consent must be given before performance of any study related procedure not part of standard medical care, with the understanding that the patient may withdraw consent at any time without prejudice to future medical care.
8. Females of childbearing potential (FCBPs) must have a confirmed negative serum pregnancy test within the 7 days prior to inclusion
9. FCBPs and male subjects who are sexually active with FCBP must agree to use highly effective concomitant methods of contraceptive during the study and for 30 days following the last study drug dose. Male subjects must use contraception and refrain from donating sperm for at least 90 days after the last dose of carfilzomib.
10. Eastern Cooperative Oncology Group (ECOG) performance status 0-2. In patients >75 years of age, performance status 0-1.
11. Patients must meet the following adequate organ and bone marrow function within 21 days prior to inclusion:
 - Absolute neutrophil count (ANC) $\geq 0,5 \times 10^9/L$ and platelet count $35 \times 10^9/L$. Platelet transfusions to help patients meet eligibility criteria are not allowed within 3 days before study enrollment. Granulocyte growth factors are allowed to meet the inclusion criteria.
12. Patient must be willing and able to adhere to the study schedule and other protocol requirements.

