8.2 Exclusion criteria

Patients meeting any of the following exclusion criteria are not to be enrolled in the study:

1. Change of first line treatment because of stable or progressive disease.
2. Female patients who are lactating or have a positive serum pregnancy test during the screening period.
3. Major surgery within 28 days before enrollment.
4. Radiotherapy within 14 days before enrollment. Glucocorticoid therapy within the 14 days prior to inclusion that exceeds a cumulative dose of 160 mg dexamethasone or 1000 mg prednisone.

5. Patients who started treatment more than 12 month before screening
6. Central nervous system involvement.
7. Uncontrolled heart disease, including congestive heart failure (NYHA III-IV), uncontrolled angina pectoris, uncontrolled conduction abnormalities, acute diffuse infiltrative pulmonary disease, pericardial disease or myocardial infarction within 6 months prior to enrollment
8. Active hepatitis B or C infection or known human immunodeficiency virus (HIV) positivity.
9. Any other serious medical or psychiatric illness that could, in the investigator's opinion, potentially interfere with the completion of treatment according to this protocol.
10. Known allergy to Captisol (a cyclodextrin derivative used to solubilize carfilzomib) or to any of the study medications, their analogues, or excipients in the various formulations of any agent.
11. Contraindication to dexamethasone or any of the required concomitant drugs or supportive treatments, including hypersensitivity to antiviral drugs, or intolerance to hydration due to pre-existing pulmonary or cardiac impairment.
12. Another active malignancy. Patients with non-melanoma skin cancer or carcinoma in situ of any type are not excluded if they have undergone complete resection.
13. Patients that have previously been treated with carfilzomib.
14. Primary plasma cell leukemia, systemic AL amyloidosis, Waldenström's macroglobulinemia, POEMS syndrome.
15. Pleural effusions requiring thoracentesis within the 14 days prior the inclusion.
16. Ascites requiring ascites puncture within the 14 days prior to inclusion.
17. Previous allogeneic transplantation
18. Uncontrolled hypertension or uncontrolled diabetes despite medication
19. Contraindication to PET-CT

20. Not expected to tolerate full dose KRd

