12.8 Study drug packaging, labeling and ordering

Carfilzomib

Study drug carfilzomib will be delivered free of charge from Amgen covered with final study label on packages based on subscriptions of each study site. Study sites

will document a drug medication diary during protocol treatment, including dose, batch number, shelf life and amount.

Lenalidomide

Lenalidomide 25mg will be taken orally with the morning breakfast. Study sites will document a drug medication diary during protocol treatment, including dose, batchnr, shelf life and amount. This drug will be reimbursed as routine medication, with labelling written locally by the treating physician in the study:

Dexamethasone

Dexamethasone 40 or 20 mg will be taken orally with the morning breakfast. Study sites will document a drug medication diary during protocol treatment, including dose, batch number, shelf life and amount. This drug will be reimbursed as routine medication, with labelling written locally by the treating physician in the study.

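### Section 12.5 words the over-75 dexamethasone dose as daily, where 20 mg on days 1, 8, 15 and 22 is evidently meant

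*Protocol*

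**What the plan says.** Protocol section 12.5 opens with the general rule: "Dexamethasone will be given on days 1, 8, 15 and 22 in cycles of 28 days, and a dose of 40 mg PO". The next sentence covers the oldest patients: "For subjects aged > 75 years, a daily low-dose dexamethasone dose of 20 mg is recommended". The dose-reduction table below it lists 40 mg as level 0 and 20 mg as level -1, without dosing days.

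Other places in the Protocol that bear on the dose:

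- **Synopsis, treatment schedule:** "The oral dexamethasone dose is 40 mg weekly throughout the study for patients under 75 years of age", followed by the fragment "20 mg for patients over 75 years of age", which has no frequency of its own.
- **Section 12.1, both tables (cycle 1 and cycles 2-4):** dexamethasone 40 mg on days 1, 8, 15 and 22. The amount stands in a per-day dose column and the days in a separate column. There is no row or note for patients over 75.
- **Section 12.8:** "Dexamethasone 40 or 20 mg will be taken orally with the morning breakfast", with no frequency for either amount.
- **Section 8.1, criterion 10:** patients over 75 can enter, with a tighter performance-status limit: "In patients >75 years of age, performance status 0-1".

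**The concern.** The age rule is meant to reduce steroid exposure in the patients least able to tolerate it. As worded, *daily* is the only frequency attached directly to the 20 mg dose, and it can be taken to mean every day of the cycle.

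Neighbouring sections use the word as a true frequency. Section 12.4, immediately before, gives maintenance lenalidomide daily. Section 12.6.1, shortly after, gives the antiviral twice daily. A reader who carries that sense into section 12.5 arrives at a dose above the standard one.

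Two features of the plan make clear wording more important here:

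- Under section 12.8, dexamethasone is supplied as routine medication and labelled locally by the treating physician. Carfilzomib, by contrast, arrives with a study label. The protocol text is therefore what the labelling physician works from.
- Section 14.7 defines overdose by reference to the dose the protocol specifies and requires overdoses to be reported as serious adverse events. That rule needs a specified dose that can be read in only one way.

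What is at stake is patient safety in a small subgroup. No endpoint, sample size or analysis depends on it.

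**Working it through.** The Protocol states no per-cycle dexamethasone total, so there is no figure of its own to reproduce. The check is dose × number of dosing days.

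**Inputs**

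- Standard dose: 40 mg on 4 days (1, 8, 15, 22) of a 28-day cycle (sections 12.1 and 12.5).
- Over-75 dose: 20 mg (section 12.5 and synopsis).
- Number of cycles: 4 (synopsis).

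**Totals**

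| Reading | Per cycle | Four cycles |
|---|---|---|
| Standard, 40 mg on 4 days | 40 × 4 = 160 mg | 160 × 4 = 640 mg |
| Over 75, 20 mg on the same 4 days | 20 × 4 = 80 mg | 80 × 4 = 320 mg |
| Over 75, 20 mg on all 28 days | 20 × 28 = 560 mg | 560 × 4 = 2,240 mg |

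**Ratios**

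- Intended to standard: 80 / 160 = 0.5.
- Every-day reading to standard: 560 / 160 = 3.5.
- Every-day reading to intended: 560 / 80 = 7.

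If a prescriber stopped at day 21, in step with lenalidomide (an assumption; no section says this), the total would be 20 × 21 = 420 mg per cycle. That is 420 / 80 = 5.25 times the intended dose and 420 / 160 = 2.625 times the standard one.

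Over any 14 days, every-day dosing gives 20 × 14 = 280 mg. For scale, exclusion criterion 4 in section 8.2 bars entry to patients who received more than 160 mg dexamethasone in the 14 days before inclusion.

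**Which reading the text supports**

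- The sentence just before fixes the days; the age sentence changes the amount.
- The synopsis fragment follows directly on a weekly regimen and naturally inherits it.
- The section 12.1 column headings make it natural to read a daily dose as the dose per dosing day.
- 20 mg is the first reduction step below 40 mg.
- Section 2.1.1 applies the low-dose label to a weekly regimen ("low-dose dexamethasone 40 mg weekly"), so 560 mg per cycle could hardly carry that label.

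All five points lead to 80 mg per cycle. None of these places, however, states the days for the 20 mg dose, and none corrects the word *daily*.

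**How many patients could be affected**

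Section 8.1 requires prior ASCT, and section 1.1 describes ASCT as standard for eligible patients below 65 to 70 years. Section 8.2 excludes "Patients who started treatment more than 12 month before screening". A patient over 75 at screening must therefore have begun first-line treatment after about 75 − 1 = 74 years of age. The Protocol gives no expected number of such patients among the 50 to be treated; it is likely to be very small and could be zero.

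**The case against.** The best reply is that the document resolves the matter itself. A prescriber would have to overlook the preceding sentence, the tables, the reduction ladder and the weekly synopsis to give dexamethasone every day.

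The Protocol's own usage gives this some support. Section 12.3.2 speaks of resuming lenalidomide at 25 mg daily although that drug is given only on days 1-21, and section 12.4 adds that dosing is continuous where no break is meant. On that pattern, *daily* refers to the scheduled days. The 7-fold and 3.5-fold figures then belong to a reading that nobody intends. In addition, dosing is supervised (section 12.9), a medication diary is kept (section 12.8), the age rule is only a recommendation, and there may be no patient over 75 at all.

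Most of this stands. It settles what was meant, and it means the multiples describe a worst case; they do not predict what will happen. The lenalidomide parallel is only partial, because days 1-21 are consecutive while the dexamethasone days are a week apart. What the reply does not remove is that the sentence, taken by itself, says something else, that the error would run in the harmful direction, and that criterion 10 makes the sentence operative. An instruction of this kind should be safe without having to be reconstructed from other sections.

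**Conclusion.** The over-75 sentence in section 12.5 is wrong as written. The intended dose is 20 mg on days 1, 8, 15 and 22. Taken literally, the wording could lead to as much as seven times that amount, and 3.5 times the standard dose, in the group it is meant to protect. The worst case assumes 20 mg on all 28 days; the Protocol gives no basis for estimating how likely the misreading is.

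The practical weight is minor, because context points to the right dose and few patients over 75 should enrol. The correction should still be made, on safety grounds. There is no consequence for the design, the sample size or the analysis.

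**What to change.** In section 12.5, replace the over-75 sentence with: *For subjects aged > 75 years, dexamethasone 20 mg on days 1, 8, 15 and 22 is recommended.* Add a footnote with the same dose and days to the dexamethasone row of both section 12.1 tables (cycle 1 and cycles 2-4).

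The cost is one corrected sentence and one footnote repeated in two tables. The intended treatment does not change.

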12.6 Concomitant treatment

A concomitant medication is defined as any prescription or over-the-counter preparation including vitamins. Concomitant medications received in conjunction with an AE/SAE will be described in the eCRF. Blood products must be reported on the appropriate eCRF.

12.6.1 Required concomitant medication

These should be initiated at least 24 hours before the first administration of carfilzomib.

Antiviral

Valacyclovir 250-500 mg PO twice daily or an equivalent acyclovir is a required medication and should be continued for the duration of study treatment.

Thromboprophylaxis

There is an increased risk of thrombosis, predominantly deep venous thrombosis and pulmonary embolism (but also myocardial infarction and cerebrovascular events) in MM patients treated with lenalidomide and dexamethasone. The decision of antithrombotic prophylaxis (acetylsalicylic acid or LMWH) during maintenance treatment needs to be considered by individual risk assessment based on prior thrombosis history, smoking, hypertension, hyperlipidemia and paraprotein status. At least ASA 75 mg per day will be given as prophylaxis for all patients. Study patients should be closely monitored for symptoms of thrombosis.

Pregnancy and contraception

Highly effective contraception methods must continue throughout the study until 30 days after the last study drug administration, in FBCPs and men having sex with FCBPs. Estrogen-containing methods cannot be used, because of lenalidomides thrombogenic potential. The following methods are considered highly effective:

- Progestogen-only hormonal contraception associated with inhibition of ovulation
- Injectable
- Implantable
- Intrauterine device
- Intrauterine hormone-releasing system (not containing estrogen)

- Bilateral tubal occlusion
- Vasectomized partner
- Complete sexual abstinence

If a menstrual period in a FCBP does not occur at the anticipated time, study drug treatment must be interrupted, and a serum pregnancy test must be performed. Study drug administration may resume after documentation of negative pregnancy test.

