Venous and arterial thromboembolic events: There is an increased risk of VTEs (predominantly deep vein thrombosis and pulmonary embolism) in MM patients treated with lenalidomide in combination with dexamethasone or other chemotherapy. There is also an increased risk of arterial thromboembolic events (predominantly myocardial infarction and cerebrovascular event). Patients with known risk factors for thromboembolism- including prior thrombosis- should be closely monitored. Action should be taken to try to minimize all modifiable risk factors (e.g. smoking, hypertension, hyperlipidemia). Erythropoietin agents and hormone-replacement therapy should be used with caution in patients receiving lenalidomide and dexamethasone. Patients and physicians are advised to be observant for the signs and symptoms of thromboembolism. Patients should be instructed to seek medical care if they develop symptoms such as shortness of breath, chest pain, arm or leg swelling.

If the patient experiences any thromboembolic events, treatment must be discontinued, and standard anticoagulation therapy started. Once the patient has been stabilized on the anticoagulation treatment and any complications of the thromboembolic event have been managed, the lenalidomide treatment may be restarted at the original dose dependent upon a benefit risk assessment. The patient should continue anticoagulation therapy during the course of lenalidomide treatment.

Renal impairment: Since lenalidomide is primarily excreted unchanged by the kidney, starting dose adjustments is recommended in patients with renal impairment. Therefore, care should be taken in dose selection and monitoring of renal function is advised in patients with renal impairment.

Thyroid function: Cases of hypothyroidism and thyroid dysfunction have been reported and monitoring of thyroid function should be considered.

Peripheral neuropathy: Lenalidomide is structurally related to thalidomide, which is known to induce severe peripheral neuropathy. At this time, the neurotoxic potential of lenalidomide associated with long-term use cannot be ruled out.

Tumour Lysis Syndrome: Because lenalidomide has anti-neoplastic activity the complications of tumour lysis syndrome may occur. The patients at risk of tumour lysis syndrome are those with high tumour burden prior to treatment. These patients should be monitored closely, and appropriate precautions taken.

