12.2.2 Carfilzomib dosing guidelines for hematologic toxicity

Hematologic toxicity

Recommended action

Thrombocytopenia

Platelets $\leq 30 \times 10^9/l$

If $10-30 \times 10^9/l$ without bleeding continue the same dose

If evidence of bleeding or platelets $< 10 \times 10^9/l$, withhold dose until platelets return to $\geq 10 \times 10^9/l$ and/or bleeding is controlled, then resume the same dose

For each subsequent drop
to $\leq 30 \times 10^9/l$

If $10-30 \times 10^9/l$ without bleeding continue at the same dose

If evidence of bleeding or platelets $< 10 \times 10^9/l$, withhold dose until platelets return to $\geq 10 \times 10^9/l$ and/or bleeding is controlled, then resume at 1 dose reduction.

Neutropenia

If $ANC \leq 0.75 \times 10^9/l$

If $ANC 0.5-0.75 \times 10^9/l$, continue at the same dose

If $ANC < 0.5 \times 10^9/l$, withhold dose until ANC returns to $\geq 0.5 \times 10^9/l$, then resume at the same dose.

For each subsequent drop to
 $\leq 0.75 \times 10^9/l$

If $ANC 0.5-0.75 \times 10^9/l$, continue at the same dose

If $ANC < 0.5 \times 10^9/l$, withhold dose until ANC returns to $\geq 0.5 \times 10^9/l$, then resume at 1 dose reduction

Neutropenic fever

If $ANC < 0.5 \times 10^9/l$, and single temperature $> 38.5^\circ C$ or temperature $> 38.0^\circ C$ more than one hour, withhold dose until ANC returns to baseline level, then resume at the same dose.

ANC = absolute neutrophil count.

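### Section 12.6.1 requires at least ASA 75 mg daily for every patient but gives no rule for withholding it when thrombocytopenia or bleeding arises on treatment

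*Protocol*

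**What the plan says.** Section 12.6.1 lists the medication that is required and is to be started at least a day before the first carfilzomib dose. For thromboprophylaxis it first says: "The decision of antithrombotic prophylaxis (acetylsalicylic acid or LMWH) during maintenance treatment needs to be considered by individual risk assessment". That assessment is to be "based on prior thrombosis history, smoking, hypertension, hyperlipidemia and paraprotein status". The next sentence sets a minimum: "At least ASA 75 mg per day will be given as prophylaxis for all patients".

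Other sections deal with low platelets, but only for the study drugs:

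- **Carfilzomib (12.2.2).** At 10-30 x10^9/l the instruction is "without bleeding continue the same dose". With bleeding, or below 10 x10^9/l, the dose is withheld until platelets are back to at least 10 x10^9/l "and/or bleeding is controlled, then resume the same dose". Repeat episodes lead to a dose reduction.
- **Lenalidomide (12.3.2).** At the first fall below 30,000/mcL: "Interrupt lenalidomide treatment, follow CBC weekly". For later falls the drug is interrupted, and the weekly count is not repeated in the text.
- **After KRd (12.4).** Lenalidomide goes on under the "approved maintenance label for post-transplant patients, i.e. 10-15 mg daily continuously", so the prophylaxis question does not end with cycle 4.

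Neither dosing table mentions ASA or LMWH.

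**The concern.** A minimum that applies to all patients and has no written exception is a poor rule for an antiplatelet drug in a trial that expects thrombocytopenia and plans for it in detail. A site that follows the text literally would give ASA to a patient with platelets of, say, 15 x10^9/l, or to one who is bleeding. A site that sensibly stops it departs from a required medication and has no written criterion for stopping or restarting, so practice may differ between centres.

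What is at stake is avoidable bleeding risk in a few patients and clarity for sites. It is not a statistical matter.

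**Working it through.** No sample size, error rate or estimate is involved, so the check is a side-by-side reading of every part of the protocol that touches ASA, platelets, bleeding or discretion.

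**1. Can the situation arise?** Yes.
- The entry floor is 35 x10^9/L (8.1, criterion 11). This is 35 - 30 = 5 x10^9/L above the level at which lenalidomide is interrupted.
- Carfilzomib runs on at 10-30 x10^9/l without bleeding. After a hold it can restart once platelets reach 10 x10^9/l, so it can be running at counts far below the entry floor.
- KRd lasts 4 x 28 = 112 days, and lenalidomide maintenance follows.

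**2. Does anything in 12.6.1 relax the ASA minimum?** No.
- The individual assessment is worded for maintenance treatment.
- Its listed factors are thrombotic risks and paraprotein status. Platelet count and bleeding history are absent.
- Because the following sentence says at least, the assessment can raise prophylaxis above ASA but cannot lower it.

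**3. Does anything elsewhere supply the exception?**

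| Place | What it covers | Supplies an on-treatment ASA hold? |
|---|---|---|
| 8.2, exclusion 11 | Contraindication to a required concomitant drug | No: acts at entry only |
| 2.3, hematological toxicity | Alertness to bleeding, especially with co-medication that promotes it | No: the action named is a possible lenalidomide reduction |
| 12.2.1 and 12.3.2, discretion clauses | Departing from the carfilzomib and lenalidomide modifications | No: not about concomitant drugs |
| Chapter headed Safety, opening paragraph | Dose interruptions for other reasons, at the physician's discretion | Not by name: the context is study treatment |
| 14.3.1 | Investigator's general duty to protect patients in connection with SAEs | Not by name: general room only |

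**4. How soon would a low count be seen?** The flow chart schedules hematology on days 1 and 15 of each cycle, so about 14 days apart (15 - 1 = 14, and 28 - 14 = 14 to the next day 1). In follow-up it is every second month. Weekly counts are written only after a first fall below 30 x10^9/l has been found.

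**5. How many patients?** This cannot be derived. Section 2.1 says grade 3 or 4 cytopenias exceeded 10% in published carfilzomib studies, but pools the cytopenias. Section 2.3 gives thrombocytopenia in 18.4% on lenalidomide and dexamethasone, with no grade. Neither is a rate of falling below 30 x10^9/l, and no bleeding rate on ASA is given.

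**The case against.** The strongest reply is that continued ASA is inferred and not written. The sentence gives a dose and a population but no duration, whereas the antiviral in the same section is expressly continued for the whole of study treatment. Investigators also have general latitude on safety, exclusion 11 removes patients with a known contraindication, and carfilzomib is withheld for bleeding in any case. Most clinicians would stop ASA without being told.

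Much of this stands, and it keeps the point small. It does not remove it. None of these provisions says when a required drug is withheld or restarted once the problem arises on treatment.

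A reader might go further in several ways that the document does not support:

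- **That the protocol orders ASA through bleeding, or contradicts its dosing tables.** It does neither. The tables are silent on ASA, and continuation follows only from the absence of a stop rule.
- **That investigators may not stop ASA.** The general safety provisions leave them room to do so.
- **That a hold could be applied and lifted within a week.** Weekly counts are tied to the first fall only, and begin only after that fall has been detected.
- **That eligibility needs changing, or that a clause on contraindications is needed at entry.** Exclusion 11 already does that work.

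It is also fair to object that 30 x10^9/l is a lenalidomide interruption level and not an established antiplatelet threshold. That stands: the document offers no threshold for ASA or LMWH, so the value is a clinical choice.

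**Conclusion.** The point holds as a minor patient-safety correction to the wording of 12.6.1. The protocol fixes an ASA minimum for everyone without an on-treatment exception, in a population where its own dosing rules foresee platelets below 30 x10^9/l and bleeding.

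The conclusion rests on the text as written and on reading the ASA sentence as applying from the start of KRd, since required medication is to begin before the first carfilzomib dose. It does not depend on any assumed frequency, and none is offered. A reader might also look for a consequence for KRd delivery or the primary endpoints. The document gives no basis for one.

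**What to change.** Keep the present ASA sentence in 12.6.1 and add after it:

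> Withhold prophylactic ASA or LMWH for clinically relevant bleeding at any platelet count, and while platelets are below a level set by the clinical leads (suggested: <30 x10^9/l, matching the lenalidomide interruption level). Resume when platelets have recovered and bleeding is controlled. Treatment-dose anticoagulation after a thromboembolic event is decided individually.

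The last sentence is needed because 2.3 says of patients restarted on lenalidomide after such an event: "The patient should continue anticoagulation therapy during the course of lenalidomide treatment". A prophylaxis hold should not be read as overriding that, nor the reverse. The text should be stated to apply both during KRd and during lenalidomide maintenance.

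The cost is three sentences, with no new visits, tests or eligibility changes. The hold would rely on the counts already scheduled, with the detection intervals shown above. The real downside is clinical: a period without thromboprophylaxis while carfilzomib and dexamethasone may continue. The clinical leads should weigh that when they confirm the platelet level.
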